 The study involves data that exist at the time of IRB submission and data that will be generated after IRB submission. Include this activity in the Methods section. Examples The study plans to conduct a retrospective chart review and ask subjects to complete a questionnaire. The study plans to include subjects previously diagnosed with a specific disease and add newly diagnosed subjects in the future. 					
The study will use data that have been collected under another IRB protocol. Include in the Methods section and enter the IRB number from which the research material will be obtained. When appropriate, note when subjects have provided consent for future use of their data and/or specimens as described in this protocol.					
Enter one IRB number per line, add more lines as needed					
Data Specimens Data & Specimens					
☐ Data ☐ Specimens ☐ Data & Specimens					
☐ Data ☐ Specimens ☐ Data & Specimens					
Data Analysis					

Power analyses may not be appropriate if this is a feasibility or pilot study, but end-point analysis plans are always appropriate even if only exploratory. Provide all information requested below, or provide justification if not including all of the information.

Data Analysis Plan:

All continuous data will be analyzed using independent 2-group t tests and reported as means \pm standard deviations. Categorical data will be compared between the 2 groups using chi-square tests and reported as counts and percentages. Nonparametric equivalents Wilcoxon rank-sum and Fisher exact tests will be used as needed for nonnormal distributions and low variable numbers, respectively. Treatment effects on outcomes will be compared between baseline versus HPE and HPE versus market competitor group with a significance level of p < 0.05.

Endpoints

Primary:

Evaluation of the tolerability of the study product.

- a. Nature, incidence, and severity of adverse events (AEs)
 - 1) Defined as any untoward or undesirable medical occurrence in the form of signs, symptoms, abnormal findings, or diseases that emerge or worsen relative to baseline (i.e., if present upon study entry) during the study regardless of causal relationship.
 - 2) Assessment
 - i. Incidence and severity of AEs (mild, moderate, severe)
 - ii. Relationship of AEs to study product (probable, possible, unlikely, unrelated)
 - 1. If possibly or probably related to the study product, determine whether related to the product itself or procedures pertaining to delivery of the study product.

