 - i) 1 Exception: Very much improved and optimal cosmetic result for the subject
 - ii) 2 Moderate: Much improved and marked improvement in condition, but not optimal for subject; touch-up would slightly improve the result
 - iii) 3 Slight: Improved with obvious improvement but touch-up or retreatment indicated
 - iv) 4 No change: Appearance essentially the same as original condition
 - v) 5 Worse: Appearance worse than original condition
 - b) Cosmetic Improvement Scale [8]: The following parameters will be scored as a percentage of total responses from participants.
 - i. Percentage of subjects satisfied or very satisfied with the treatment
 - ii. Percentage of subjects who would recommend the treatment to a friend
 - iii. Percentage of subjects reporting high likelihood of continuing treatment
 - iv. Percentage of subjects reporting treatment positively or negatively affected self-esteem
 - v. Percentage of subjects reporting no, minimal, moderate, or significant improvement in fine lines and wrinkles, skin tone, skin smoothness and/or puffiness

Data collection

Data collection, processing, transmission, and storage will follow Mayo Clinic Data Protection Standards. Redcap, a Mayo-endorsed, password protected HIPAA-compliant system, will be used as the electronic data collection and management system. It allows data tracking and downloads to statistical analysis packages. Participant informed consents will be tracked using Ptrax. Participant questionnaires will be collected using REDCap.

Canfield VISIA CR Gen 5 with 3DPrimos will be used to evaluate qualitatively and quantitatively skin profile changes. If Canfield is processing any data on behalf of Sponsor, Canfield shall do so in strict accordance and compliance with applicable laws, rules, and regulations, including to the extent applicable, the Health Insurance Portability and Accountability Act of 1996 and the Regulation (EU) 2016/679 of the European Parliament and the Council of 27 April 2016 on the protection of natural persons with regard to the processing of personal data and on the free movement of such data (GDPR), and with Sponsor's instructions, and it shall not utilize said data for any other purpose whatsoever without obtaining data subject's consent first.

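### The Data Analysis Plan names no ordinal method, so the graded self-assessment answers most naturally go to a chi-square test or a percentage cut that ignores their order, at a cost in power where answers are given per hand

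*Combined protocol and SAP*

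**What the plan says.** The Data Analysis Plan gives continuous outcomes an independent two-group t test. For the rest, "Categorical data will be compared between the 2 groups using chi-square tests and reported as counts and percentages". The fallbacks are tied to two conditions: "Nonparametric equivalents Wilcoxon rank-sum and Fisher exact tests will be used as needed for nonnormal distributions and low variable numbers, respectively". Treatment effects are to be compared for baseline against HPE, and for "HPE versus market competitor group with a significance level of p < 0.05". No trend test, proportional-odds model or other ordinal method appears.

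Secondary endpoint 2 (self-assessment) consists largely of graded answers:

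- **GAIS (2a)** has five numbered grades. Grade 1 is the best result, and the scale ends with "4 No change: Appearance essentially the same as original condition" and "5 Worse: Appearance worse than original condition".
- **Cosmetic Improvement Scale (2b)** has the general rule "The following parameters will be scored as a percentage of total responses from participants". Item i is "Percentage of subjects satisfied or very satisfied with the treatment". Item v is "Percentage of subjects reporting no, minimal, moderate, or significant improvement in fine lines and wrinkles", and it continues with skin tone, smoothness and puffiness.

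Under Study procedures, 80 subjects apply HPE to the right dorsal hand and the competitor to the left. The face and decolletage receive HPE only.

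**The concern.** A chi-square test on several grades asks whether two distributions differ in any way at all. It spreads its power over patterns of no interest, and it can be significant without either product being better. Fisher's exact test on the same table also ignores order. Cutting satisfaction at its top two answers treats the two as equal and discards differences below the cut.

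Comparison with the competitor is a stated aim. GAIS rates change from the original condition, so it has no baseline value to test, and the between-product comparison is the planned contrast that fits it. A real difference in self-rated improvement would be more likely to be missed, although the graded answers would already have been collected. This is separate from whether the two hands are analysed as paired.

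**Working it through.** **Plan figure.** The plan states no power, effect size or sample-size derivation, so there is nothing to reproduce.

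**Which test each item gets**

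| Item | Form | Track on the natural reading |
|---|---|---|
| GAIS | 5 ordered grades, not classified | probably chi-square, 4 df; a t test or rank-sum is possible |
| Item v | 4 ordered levels, each reported | chi-square, 3 df |
| Item i | graded answer cut to one percentage | chi-square, 1 df |

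**Inputs from the documents:** 80 right hands (HPE), 80 left hands (competitor), level 0.05.

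**Assumed inputs:** two-sided test; no dropout; a common odds ratio (OR) of 1.5, 2.0 or 2.5 across grades; independent hands; and these reference splits:
- GAIS 5/20/40/30/5%
- item v 15/30/35/20% (none to significant)
- satisfaction 20/35/30/10/5% (the response form is not in the documents, so five levels is itself an assumption)

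**Worked case: item v, OR 2.0.** From the best level down, the reference cumulative percentages are 20, 55 and 85, with odds 0.25, 1.222 and 5.667. Doubling the odds gives 33.3, 71.0 and 91.9%. The level percentages are therefore p = 20/35/30/15 and q = 33.3/37.6/20.9/8.1.

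- *Chi-square.* The noncentrality is n·Σ(p−q)²/(p+q) = 80 × (0.0333 + 0.0010 + 0.0162 + 0.0205) = 5.68. On 3 df (critical value 7.81) the power is about 49%.
- *Rank-sum.* V = 2n³/[3(2n+1)²] × (1 − Σm³), where m is the mean of p and q. This gives V = 13.17 × (1 − 0.0849) = 12.05. Then z = ln 2 × √12.05 = 2.41, and the power is Φ(2.41 − 1.96) = 67%.

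The two tests see almost the same signal (5.68 against 2.41² = 5.8). The loss arises because chi-square needs 7.81 for significance, whereas a one-df ordered test needs 3.84.

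**Worked case: satisfaction, OR 2.0.** The top-two percentages are 55% and 71.0%. The standard error is √(0.55×0.45/80 + 0.71×0.29/80) = 0.0753. So z = 0.160/0.0753 = 2.12, and the power is Φ(0.16) = 56%, against about 67% for rank-sum on all five levels.

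**Simulated power, independent hands (3,000 runs per setting)**

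| Item | Comparison | OR 1.5 | OR 2.0 | OR 2.5 |
|---|---|---|---|---|
| GAIS | chi-square → rank-sum | 17 → 29% | 45 → 66% | 70 → 89% |
| Item v | chi-square → rank-sum | 20 → 30% | 50 → 68% | 76 → 88% |
| Satisfaction | top-two cut → rank-sum | 22 → 29% | 54 → 66% | 79 → 89% |

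Repeat simulations agreed within about 2 points. With no true difference, rank-sum rejected in 4.8 to 5.3% of runs.

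**Other assumptions**

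- *A flatter GAIS split* (10/20/30/30/10%): chi-square loses 12, 23 and 17 points at OR 1.5, 2.0 and 2.5. A cut after grade 2 loses 6, 13 and 10.
- *Larger effect:* at OR 3.0 the best cut loses only 4 to 6 points.
- *Cut at the end of the scale:* the loss can be 15 to 57 points at OR 1.5 to 2.0.
- *50 responses per hand:* for a four-level item at OR 1.5, the chi-square loss is about 7 points.
- *Paired tests* (satisfaction, within-person correlation 0.3): from McNemar on the cut to signed-rank on all levels, power rises from 30 to 37%, 66 to 78% and 85 to 94%. Order therefore matters after pairing as well. This was shown for satisfaction only.

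**The case against.** **The plan does not say that these answers will be tested as unordered categories.** A reader might infer that as fact. But GAIS is numbered 1 to 5 and never assigned to a track. Read as a score, it gets a t test or rank-sum, and the loss disappears: with the GAIS split above, the t test has 27, 66 and 88% power against 28, 67 and 89% for rank-sum. This stands for GAIS. It does not help item v or the satisfaction cut, which are defined as percentages, the reporting format of the categorical track. Nor does the rank-sum clause clearly cover sparse grades. A 5% grade among 80 responses is 4 people, and low numbers lead to Fisher's test.

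**The between-product comparison may not exist for these endpoints.** The self-assessment text never mentions hands, and the satisfaction item refers to a single treatment. Figure 1 appears to list questionnaires for the competitor hand at weeks 0, 6 and 12. Week 0 cannot hold an improvement rating, so this may be a generic visit list. Nothing places the competitor at weeks 26 and 52. This stands: if answers cover the whole subject, no such test can be run and no power is lost.

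**The top-two percentage is a legitimate, readable summary, and item v is reported by level rather than collapsed.** Both are true. They support keeping the percentages as descriptions, but not testing on them alone.

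**The magnitudes rest on assumed splits and on independent hands.** This also stands. A fixed loss should not be read out of these figures.

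**Conclusion.** The point holds as a gap in the analysis plan. Ordered self-assessment answers have no ordinal test assigned, and the rule that most naturally applies to item v, and probably to GAIS, ignores order. Satisfaction is explicitly cut. Where answers are collected per hand, the secondary HPE-versus-competitor comparison loses roughly 10 to 23 points of power with chi-square and 5 to 13 with a mid-scale cut. That range assumes 80 responses per hand, independent hands, proportional odds with OR 1.5 to 2.5, and assumed response splits. It illustrates the size of the loss and does not bound it.

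The documents do not support the stronger conclusions that all these items are certain to be tested as unordered, or that power is lost at every time point. Only secondary endpoints are affected, and the primary tolerability and photoaging endpoints are not. The change is worth making, and confidence is medium.

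**What to change.** Add a third track to the Data Analysis Plan. It should state that ordered self-assessment responses collected for both hands (GAIS grades, satisfaction and improvement levels) will be compared on their full ordered scale with a paired ordinal method. Two options are suitable:

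- an ordinal logistic model with a subject random effect, which uses order alone; or
- the Wilcoxon signed-rank test with Pratt handling of zero differences, noting that it treats the spacing between grades as comparable.

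Reserve chi-square, Fisher or McNemar for unordered or yes/no items, such as whether the subject would recommend the treatment. In the self-assessment endpoint:

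- state whether each questionnaire is answered separately for each hand, and at which visits;
- keep the listed percentages as descriptive summaries, and store the graded answer behind each one;
- treat answers that cannot be attributed to a hand or product as descriptive.

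The analysis change is wording only and needs no new visits or patients. The small downside is that an ordinal effect is slightly harder to explain than a percentage, which is why the percentages stay.

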Lauded for its superior antioxidant benefits, this highly potent form of pure vitamin C helps neutralize free radicals and protect against oxidative stress while providing visible anti-aging henefits

1% alpha tocopherol

This pure form of vitamin E neutralizes free radicals and replenishes skin lipids. It has been proven to act synergistically with vitamin C.

0.5% ferulic acid

A plant-based antioxidant, ferulic acid neutralizes free radicals and enhances the antioxidant benefits and stability of vitamins C and E.

Learn more about L-ascorbic acid

Learn More About Ferulic Acid

See All Ingredients

aqua / water / eau, ethoxydiglycol, ascorbic acid, glycerin, propylene glycol, laureth-23, phenoxyethanol, tocopherol, triethanolamine, ferulic acid, panthenol, sodium hyaluronate

Study Design and Methods

Methods: Describe in lay terms, completely detailing the research activities that will be conducted by Mayo Clinic staff under this protocol.

80 participants over the age of 40 with moderate photoaging (dyschromic facial skin with fine lines and wrinkles) will be recruited from Mayo Clinic Center for Aesthetic Medicine and Surgery (CAMS) to participate in this study. After signing written informed consent, eligible subjects will be instructed to apply topical HPE to entire face and decolletage twice daily, in the morning and at bedtime. In addition, subjects will be instructed to apply topical HPE to the right dorsal hand and market-competitor group (SkinceuticalsTM C.E. Ferulic) to left dorsal hand. Select subjects (n=20) will also apply topical HPE to the right upper inner arm for skin biopsies at week 12. A baseline skin biopsy will be obtained from untreated skin on the left upper inner arm from the same subjects. Subject renumeration will be provided for skin biopsies.

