We will enroll an additional 50 patients as part of a substudy. We aim for 30-40% people of color. We will partner with DMC BIPOC entrepreneur (MotivateMe) for community outreach and engagement. They will have the same study visits and surveys at baseline, 6 weeks, and 12 weeks. Biopsies will be optional and can be done on the left forearm and/or upper inner arm at baseline and at 12 weeks. At 12 weeks the biopsy

will be on the right arm in a similar area as the left. Participants will receive \$250 for each biopsy. All subjects will have microbiome (swab and tape) at baseline and 12 weeks. All subjects will have standard face/neck photography and 3D imaging at all three visits. Subjects in this 2X study will be reimbursed \$50 for the first two study visits. They will receive \$100 for the 12 week visits. Same inclusion and exclusion criteria. We will ask males to be shaved for their photos.

Participants will be given the option to return to the clinic for photos at 6 months and 12 months. These participants will be given another bottle of the study product.

We will pursue collaboration with MotivateMe, LLC local Latinx/Hispanic entrepreneur for skin of color patient recruitment. This is a collaborative effort with Center for Health Equity and Community Engagement Research

We have been approached by the Rochester Post Bulletin for an article regarding our clinical study and skin of color patient recruitment. This has been vetted by Mayo Pubic Affairs team, but there is concern that IRB may consider this article as a recruitment tool. We will also use social media (see social media plan attachment)

Subject Information

Target accrual is the proposed total number of subjects to be included in this study at Mayo Clinic. A "Subject" may include medical records, images, or specimens generated at Mayo Clinic and/or received from external sources.

Target accrual: 80 + 50 from substudy = 130

Subject population (children, adults, groups):

Adults age 40 to 85 years with moderate photoaging.

Inclusion Criteria:

- 1. Adult males and females ages 40 to 85 years

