Additionally, Canfield shall take all appropriate technical and organizational measures which are necessary to prevent the unauthorized or unlawful processing of, the unauthorized or unlawful disclosure of and/or the accidental loss or destruction of, or damage to, such data, including without limitation, implementation and enforcement of administrative, technical and physical security policies and procedures. Incident Reporting. Canfield shall promptly notify Sponsor in the event of a security breach or incident involving any data which Canfield is processing on behalf of Sponsor.

Study procedures

The skin biopsies, skin swabs and long-term follow-up visits will be obtained separately from 80 subjects.

- n=80 subjects
- Entire face and decolletage HPE (n=80)
- HPE (n=80) to be applied on the right dorsal hand
- Skinceuticals CE Ferulic (n=80) to be applied on the left dorsal hand
- Skin biopsy (baseline): Left upper inner arm untreated (n=30)
- Skin biopsy (week 12): Right upper inner arm HPE treated (n=30, same subjects as above)
- Microbiome analysis (baseline): Left and right malar cheek untreated (n=80 with both skin swab and tape-stripping method)
- Microbiome analysis (week 12): Left and right malar cheek HPE treated (n=80 with both skin swab and tape-stripping method)

N=30 - Skin biopsy: Two total skin biopsies will be performed per subject (n=30 subjects). In this study, we will remove a small piece of skin from untreated skin on the left upper inner arm (baseline) and HPE treated area on the right upper inner arm (week 12). This is called a skin biopsy.

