Informed consent must be obtained with signing of the ICF prior to performing any study-related procedure.

Assessments during the screening visit will include:

- Demographic data
- Medical and surgical history
- Medication history
- Concomitant medication
- Concomitant procedures
- Physical examination

Based on the result of the screening visit and review of the eligibility criteria, the PI will assess each potential subject's eligibility for study inclusion. If the subject is found eligible, she can then be enrolled. The screening visit results will be recorded in the subject's electronic case report form (e-CRF) and the subject will be scheduled for a subsequent visit to complete additional baseline assessments,

Enrolled subjects will then initiate baseline visit (V0) at the same time during which they will complete their baseline assessments and initiate their treatment.

General assessment

- Baseline VISIA-CR imaging
- Photography
- Skin microbiome facial swab and tape-stripping (n=80 skin swab and tape-stripping)
- Skin biopsy (n=30)
 - o Left upper inner arm (untreated skin)

Treatment

- Treatment: Topical HPE twice daily for study duration.
- Study staff will demonstrate treatment application.
- Subject instructions and treatment log will be provided.
- Each subject will receive the first cosmetic kit, which will include gentle cleanser, unscented bar soap, HPETM product, SkinceuticalsTM CE Ferulic serum, sunscreen and moisturizer. A second cosmetic kit will be provided at week 6 visit.

• For questions, subjects will be provided contact email: [contact]

Visit 1: Follow-up at 6-weeks

- VISIA-CR imaging
- Photography
- Topical treatment jars will be weighed to ensure correct application amount.
- Subject treatment log will be reviewed.

Specific assessment (cosmetic evaluation questionnaires)

- Global Aesthetic Improvement Scale
- Cosmetic Improvement Scale

Treatment assessment

- Continuation of Topical HPE twice daily as indicated.
- Study staff will re-demonstrate treatment application.
- Each subject will receive their second cosmetic kit, which will include gentle cleanser, unscented bar soap, HPETM product, SkinceuticalsTM CE Ferulic serum, sunscreen and moisturizer.
- For questions, subjects will be provided contact email: [contact]

Visit 2: Follow-up at 12-weeks

- VISIA-CR imaging
- Photography
- Skin microbiome facial swab and tape-stripping (n=80 skin swab and tape-stripping)
- Skin biopsy (n=30)
 - Right upper inner arm (HPE)

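### The face has no concurrent control, yet its change from baseline is labelled a treatment effect, and same-subject comparisons are assigned independent-samples tests

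*Combined protocol and SAP*

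**What the plan says.** **Who receives what on the face.** In Study Design and Methods, "eligible subjects will be instructed to apply topical HPE to entire face and decolletage twice daily". Study procedures gives n=80 for this, which is the whole main study. C E Ferulic goes on the left dorsal hand only, and HPE on the right. No vehicle, untreated, delayed-start or split-face control is described. For the 2X amendment, "We will enroll an additional 50 patients as part of a substudy", and "All subjects will have standard face/neck photography and 3D imaging at all three visits"; no control is described there either.

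**What else changes at the start.** At the baseline visit each main-study subject receives the "first cosmetic kit, which will include gentle cleanser, unscented bar soap, HPETM product, SkinceuticalsTM CE Ferulic serum, sunscreen and moisturizer". Inclusion criterion 6 requires other anti-aging treatments to stop for the duration of the study.

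**How the data are to be analysed.** The Data Analysis Plan says: "All continuous data will be analyzed using independent 2-group t tests". Its fallback is: "Nonparametric equivalents Wilcoxon rank-sum and Fisher exact tests will be used as needed". It then says: "Treatment effects on outcomes will be compared between baseline versus HPE", alongside HPE against the competitor, at p < 0.05. No paired t test, signed-rank test, McNemar test or repeated-measures model appears. The photoaging endpoint, listed under Primary, is change from baseline at 6, 12, 26 and 52 weeks.

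**What is to be concluded.** The hypothesis in Research Question and Aims is that HPE is effective for facial rejuvenation, and one aim is to assess its effect on lines, tone, erythema and pigmentation. The Methods section describes the long-term follow-up as an analysis of topical HPE on the face and decolletage. The study title, by contrast, speaks of a regimen that contains HPE.

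**The concern.** There are two separate faults.

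The first is attribution. When every face is treated, the change from baseline combines whatever HPE does with whatever else happens over the same period: newly issued skin-care items, any withdrawal of other products, and time. Nothing in the facial data separates these. If the contrast is called a treatment effect, a significant change can be reported as showing that HPE works on the face, which is the study's hypothesis.

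The second is the test. Baseline and follow-up values come from the same people, as do the right and left hands and the two biopsies. An independent-samples test discards that pairing and uses a standard error that is wrong for these data, so the P values are wrong whenever the paired values are correlated.

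**Working it through.** **Attribution.** No arithmetic applies; the sections are set side by side.

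- Study Design and Methods and Study procedures: HPE on every face, comparator on one hand only. The facial contrast has no concurrent reference.
- Baseline visit and inclusion criterion 6: other items are introduced, and other products may be withdrawn, when HPE starts.
- Data Analysis Plan: the resulting contrast is listed as a treatment effect, and no sentence limits that reading.

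A before-after difference in this setting estimates the total change during the regimen. The share due to HPE cannot be identified, whichever test is used.

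**Choice of test.** The plan gives no power calculation, SD or within-subject correlation, so there is no figure to reproduce.

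*Inputs.* From the documents: n = 80 and significance level 0.05. Assumed: a two-sided test (sidedness is not stated), complete data on all 80, the same SD s at both times, and r = 0, 0.5 or 0.8.

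*Smallest observed mean change that reaches significance, in units of s:*

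- Independent test: t(0.975, 158) × √(2/80) = 1.975 × 0.1581 = **0.312**, whatever r is.
- Paired test: the SD of the change is s√(2(1−r)), so the threshold is t(0.975, 79) × √(2(1−r)) / √80, with t = 1.990.

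| r | √(2(1−r)) | Paired threshold | Independent threshold |
|---|---|---|---|
| 0 | 1.414 | 0.315 | 0.312 |
| 0.5 | 1.000 | 0.223 | 0.312 |
| 0.8 | 0.632 | 0.141 | 0.312 |

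*Rejection rate of the independent test when nothing changes.* The true standard error is smaller than the assumed one by the factor √(1−r), so the rate is about 2[1 − Φ(1.96/√(1−r))].

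- r = 0.5: 1.96/0.707 = 2.77, giving 0.56%.
- r = 0.8: 1.96/0.447 = 4.38, giving about 0.001%.

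A simulation of 20,000 trials per setting gave 0.59% and 0.01% for the independent test, and 5.0% and 5.3% for the paired test.

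**How the two faults interact.** At r = 0.8, an observed mean change between 0.14 and 0.31 baseline SD is significant with the paired test and not with the independent one. That holds whatever caused the change. Correcting the test alone therefore makes a shift unrelated to HPE more likely to be declared significant under the treatment-effect label.

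**The case against.** The strongest reply is that this is a modest cosmetic study, with tolerability listed first among its primary endpoints and a title that already refers to a regimen. An uncontrolled facial evaluation is legitimate in that setting. That stands as a defence of the design, and no facial control arm is asked for here. It does not defend the label in the analysis plan, because the hypothesis, the aim and the long-term wording all attribute the change to HPE.

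The protocol also narrows the alternative explanations. Study constraints 4 and 5 hold way of life, physical activity and diet constant. Exclusion 10 removes people expecting intensive sun or tanning. Exclusion 11 removes recent users of prescription vitamin A derivatives, and exclusion 2 removes those with recent aesthetic treatment, so fewer subjects may have a product to withdraw. These are real mitigations, but they do not replace a control.

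The hand comparison has a concurrent comparator within each subject, so time and subject-level influences are largely shared between hands. Exclusion 5 removes marked asymmetry, which softens the objection to fixed sides. This is a real strength. But it compares HPE with another active product, on hands, and cannot be carried over to the face.

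A reader might infer that the 2X participants also receive the kit. The amendment does not say so, nor does it state their application site. The point about that substudy is only that it images the face and describes no control.

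**Conclusion.** The point holds and should be corrected. The facial and decolletage results are uncontrolled before-after changes during use of an HPE-containing regimen, and the plan's treatment-effect wording goes beyond what the design can show. The independent-samples tests are wrong for every same-subject comparison. With positive correlation they are conservative: at n=80 the threshold is 0.31 baseline SD, where a paired test needs 0.22 (r=0.5) or 0.14 (r=0.8), and false rejection is about 0.6% or near zero instead of 5%. These figures rest on assumed correlations, equal SDs, complete data and two-sided testing. At r=0 the two tests barely differ.

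Three stronger readings are tempting, and the documents do not support them. A reader might infer that the facial result is known to be biased in favour of HPE; the documents give neither the size nor the direction of any non-HPE change. A reader might infer that the planned test produces too many false positives; with positive correlation it produces too few. A reader might infer that the whole study is uncontrolled; the hands do have a concurrent comparator.

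**What to change.** Make changes 1 and 2 together.

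1. **Data Analysis Plan, tests.** For every same-subject comparison (baseline against follow-up; HPE hand against C E Ferulic hand, compared on change from baseline; baseline against week-12 biopsy), use a paired t test or Wilcoxon signed-rank test and report the within-subject mean difference with a 95% CI. For same-subject categorical comparisons, use McNemar or another matched test in place of chi-square or Fisher.
2. **Data Analysis Plan, wording.** Replace the baseline-versus-HPE treatment-effect phrase with: *Change from baseline during use of the HPE-containing regimen will be estimated; for face and decolletage, including the 2X substudy, this is an uncontrolled before-after change and not an estimate of the effect of HPE.* Align the facial hypothesis and the effect-of-HPE aim in Research Question and Aims, and the long-term analysis wording in the Methods section, with that sentence.
3. **Hands.** State that the hand comparison supports only a relative statement, HPE against C E Ferulic, for hands. Note that sides are fixed, although exclusion 5 removes marked asymmetry.

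The cost is reworded text and a narrower facial claim. Visits, sample size and procedures do not change.
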